## 4.2. Exclusion Criteria

A subject who meets any of the following criteria is not eligible for study enrollment:

1. Subject has a known systemic illness known to produce autonomic neuropathy, including but not limited to amyloidosis and autoimmune neuropathies. Subject has diabetes mellitus and diagnosis of PAF. Subject with diabetes mellitus and either MSA or PD, will be evaluated on a case by case basis by the medical monitor and considered ineligible unless they meet all of the following criteria:
  - a. Well controlled type-2 DM in treatment with only oral medications and diet
  - b. HgbA1C of  $\leq 7.5\%$  performed during screening or up to 12 weeks before screening
  - c. No clinically evident peripheral neuropathy (e.g., normal sensory examination on peripheral extremities),
  - d. No known retinopathy (e.g., annual ophthalmic exam is sufficient)
  - e. No nephropathy (e.g., absence of albuminuria and GFR  $>60$ )
2. Subject has a known intolerance to other NRIs or SNRIs.
3. Subject currently uses concomitant antihypertensive medication for the treatment of essential hypertension.
4. Subject has used strong CYP1A2 inhibitors or inducers within 7 days or 5 half-lives, whichever is longer, prior to randomization or requires concomitant use until the follow-up visit.
5. Subject has changed dose, frequency, or type of prescribed medication for orthostatic hypotension within 7 days prior to randomization visit.
  - Midodrine and droxidopa (if applicable) must be tapered off at least 7 days prior to randomization.
6. Subject has a known or suspected alcohol or substance abuse within the past 12 months (DSM-IV-TR® definition of alcohol or substance abuse).
7. Subject has a clinically unstable coronary artery disease, or major cardiovascular or neurological event in the past 6 months.
8. Subject has used any monoamine oxidase inhibitor (MAO-I) within 14 days prior to randomization.
9. Subject has a history of untreated closed angle glaucoma, or treated closed angle glaucoma that, in the opinion of an ophthalmologist, might result in an increased risk to the subject.
10. Subject has any significant uncontrolled cardiac arrhythmia.
11. Subject has a Montreal Cognitive Assessment (MoCA)  $\leq 23$ .
12. Subject is unable or unwilling to complete all protocol specified procedures including questionnaires.
13. Subject had a myocardial infarction in the past 6 months or has current unstable angina.

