#### 7.1.1. Adverse Event

An AE is any untoward medical occurrence in a subject or clinical trial subject administered a pharmaceutical product that does not necessarily have to have a causal relationship with this treatment. An AE can therefore be any unfavorable and unintended sign (including an abnormal laboratory finding), symptom, or disease temporally associated with the use of a medicinal product, whether or not related to the medicinal product.

- AEs may be new events.
- AEs may be preexisting events that increase in frequency, severity, or change in nature or seriousness during or as a consequence of participation in clinical studies.
- AEs may be pre- or posttreatment complications that occur as a result of a protocol-mandated procedure (such as a biopsy).
- AEs may be clinically significant changes from baseline in physical examination, laboratory tests, or other diagnostic investigation (e.g., laboratory results, x-ray findings).
- AEs may result from an overdose of the study medication.

Whenever possible, the diagnosis (rather than a series of terms related to a diagnosis) should be recorded as the AE term.

An AE does not include the following:

- Medical or surgical procedures (such as surgery, endoscopy, tooth extraction, or transfusion); the condition that leads to the procedure is an AE
- Pre-existing diseases or conditions present or detected before signing an informed consent form that do not worsen
- Situations where an untoward medical occurrence has not occurred (such as hospitalization for elective surgery or social and/or convenience admissions)
- Overdose of either study medication or concomitant medication without any signs or symptoms, unless the subject is hospitalized for observation

Any medical condition or clinically significant laboratory abnormality with an onset date prior to the time the subject signed the informed consent form is considered to be preexisting and should be documented in the medical history CRF.

Pregnancy is not an AE; however, if a female subject becomes pregnant during the conduct of the study, the sponsor will be notified according to the procedures for SAE reporting as outlined in Section 7.4.3. Follow-up information regarding the outcome of the pregnancy and any fetal or neonatal sequelae will be obtained and documented.

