#### 7.1.4. Adverse Event of Special Interest

- At each study visit, the Investigator (or designee) will specifically query for any AESIs. The following events are considered AESIs for this study:
  - Supine hypertension
  - Cardiovascular events (myocardial infarction, cerebrovascular accident, cardiac arrhythmia, congestive heart failure)
  - Convulsion
- All AESIs must be reported to Sponsor Clinical Safety and Pharmacovigilance within 24-hours of awareness by the Investigator or his/her designee.

The AESI Report Form must be completed in accordance with the AESI Report Form Completion Guidelines. If all information on the AESI Report Form is not available at the time of the initial report, follow-up AESI reports will be completed and submitted.

To report an AESI, complete and send the AESI Report Form to the following:

Theravance Biopharma Clinical Safety

[REDACTED]

For medical questions regarding an AESI, contact the medical monitor by telephone as follows:

Medical Monitor Contact Information:

[REDACTED]

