### 8.6.2. Adverse Event Data

The AEs will be coded to the preferred terms (PTs) of the Medical Dictionary for Regulatory Activities (MedDRA®). Summaries will present by system organ class (SOC), preferred term, and severity (mild, moderate, severe), the number and percentage of subjects for whom events were reported.

In general, a treatment-emergent adverse event (TEAE) will be defined as any AE that begins on or after the date and time of the first dose of study medication and up to the date of last dose of study medication plus the number of days in the follow-up period.

The number and percentage of subjects who experience TEAEs will be summarized. Summaries of TEAEs will include the following:

- [REDACTED]
- [REDACTED]
- [REDACTED]
- [REDACTED]
- [REDACTED]
- [REDACTED]
- [REDACTED]
- [REDACTED]
- [REDACTED]

All AEs reported will be listed by subject. A listing will be provided for all subjects who experience an SAE. Listings will also be provided for subjects who discontinued study treatment prematurely because of AEs and subjects who temporarily interrupted study treatment because of AEs. The AESIs, as described in Section 7.1.4, will be listed and summarized.

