**Table 3: Electrocardiogram Test Outlier Thresholds**

Heart Rate (bpm)	Heart Rate Change From Baseline (bpm)	PR Interval (msec)	PR Percentage Change From Baseline (%)	QRS Interval (msec)	QT c F (msec)	QT c F Change From Baseline (msec)
>120	≥20	≥200	≥15	≥120	Males:	≤30
>130	≥30	≥220	≥25		<430	>30, ≤60
					≥430	>60
					≥450	
					≥470	
					≥480	
					≥500	
					Females:	
					≤450	
					≥450	
					≥470	
					≥480	
					≥500	

In addition, QTcF (msec) will also be summarized by the following categories: Normal (males <430, females <450), Borderline (males [ $\geq$ 430, <450], females [ $\geq$ 450, <470]), and Prolonged (males  $\geq$ 450, females  $\geq$ 470).

All recorded ECG interval values and ECG assessments will be presented in a by-subject listing. A separate listing of subjects with extreme values or changes, as specified in the SAP (e.g., values of QTcF  $\geq$ 450 msec if male or  $\geq$ 470 msec if female, QTcF increases from baseline >60 msec) will be provided.

Treatment-emergent ECG abnormalities are defined as those not present at baseline, or those that worsened after treatment, e.g., borderline at baseline but were prolonged after treatment.

When multiple values exist for the same nominal time point (e.g., triplicate reading), the average of the readings taken for ECG parameters will be used in the data analysis, including the outlier analysis stated below.

Cumulative distribution plots will be provided for maximum change in QTcF by day.

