9.1. Adverse Events

Adverse events are collected from signing of the informed consent through the end of follow-up. Adverse events will be coded to the preferred terms of the Medical Dictionary for Regulatory Activities (MedDRA®, version 24.0).

A treatment-emergent adverse event (TEAE) will be defined as any AE that begins on or after the date of first dose of study drug up to 14 days after the date of last dose of study drug. However, for patients who continued into Study 0170, any AE occurs after Study 0170 Visit 1 (Study 0169 Visit 6) will be considered as a TEAE for Study 0170 and will not be included in the AE summary for Study 0169 to avoid double counting.

AEs observed during the period from obtaining informed consent to the start of administration of study drug will not be considered as TEAEs and will be listed only.

AEs and TEAEs will be listed by subject. In addition, subjects with AEs leading to permanent or temporary discontinuation of treatment will be listed separately.

TEAEs will be summarized overall with counts and percentages of subjects with the events, by treatment group, system organ class, and preferred term. TEAEs leading to permanent or temporary discontinuation of treatment, related to study treatment (i.e., any reported as related), serious TEAEs, frequent TEAEs (defined as >3% in the study population), TEAEs by severity, TEAEs of special interest, deaths, and TEAEs by maximum severity and causality will be summarized.

If no adverse events meeting a specific table criterion are observed, the summary table will indicate that there were no occurrences.

9.1.1. [REDACTED]

[REDACTED]

[REDACTED]

[REDACTED]

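### The TEAE definition goes by onset date alone, so whether on-drug worsening of a screening-period AE reaches the TEAE tables depends on how the site records it

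*SAP*

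**What the plan says.** SAP 9.1 takes as a TEAE "any AE that begins on or after the date of first dose of study drug up to 14 days after" the last dose. Subjects who enter Study 0170 have later events assigned to that study. AEs observed from consent until dosing starts "will not be considered as TEAEs and will be listed only". Protocol 8.6.2 also goes by onset, covering "any AE that begins on or after the date and time of the first dose of study medication", and is introduced as a general rule. SAP 2 makes the SAP the final authority on analyses.

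The AE summaries promised in SAP 9.1 are almost all expressed as TEAEs: overall by system organ class and preferred term, serious, related, leading to discontinuation, of special interest, frequent (above 3%), by severity, and by maximum severity and causality. Deaths are the only item not worded that way.

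Three protocol sections deal with worsening at the recording stage. Section 7.1.1 says "AEs may be preexisting events that increase in frequency, severity, or change in nature or seriousness". Section 6.4.10.3 has conditions that worsen after consent recorded as an AE, and 6.4.10.10 has neurological findings that worsen during treatment reported as AEs.

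For ECG findings, the protocol text with Table 3 builds worsening into the definition itself: "Treatment-emergent ECG abnormalities are defined as those not present at baseline, or those that worsened after treatment".

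**The concern.** AEs are collected from consent, Visit 1 falls between Day -28 and Day -7, and first dose is the morning after Visit 2. There is therefore a pre-dose period of a week to about four weeks in which AEs can start and still be open at dosing. Two features of the trial make such AEs plausible. Events of special interest are actively sought from screening onward ("At each study visit, the Investigator (or designee) will specifically query for any AESIs"). Existing pressor treatment is also withdrawn before randomization ("Midodrine and droxidopa (if applicable) must be tapered off at least 7 days prior to randomization").

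If one of these AEs becomes severe or serious on study drug, it is on-treatment safety information and belongs in the comparison of arms. Under an onset-only rule, its place in the tables depends on whether the site starts a new record or continues the old one. Two subjects with the same clinical course could be counted differently. The SAP tables could also disagree with each other. Under SAP 7.2, a subject who stops drug because a screening-onset AE worsened counts as discontinued for an adverse event, yet may be missing from the table of TEAEs leading to discontinuation.

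**Working it through.** No arithmetic applies, because the documents give no figure on this point. The check is to follow each type of event through the recording rules and then through the SAP 9.1 definition.

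1. **Condition with onset before consent, worsens on drug.** Protocol 7.1.1 treats onset before consent as preexisting and sends it to medical history. Its worsening is an AE under 7.1.1 and 6.4.10.3. The AE record first arises after dosing, so it is a TEAE. No gap.
2. **AE starts after consent, does not worsen on drug.** It has pre-dose onset and is listed only. This is appropriate.
3. **AE starts after consent, is open at first dose, worsens on drug, and the site opens a new record dated from the worsening.** Onset is after first dose, so it is a TEAE and enters the tables.
4. **Same event as in 3, but the site keeps the original record.** Onset stays before first dose. It is not a TEAE and is listed only.

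Cases 3 and 4 are clinically identical, so the question is whether the visible text rules out case 4.

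- Section 7.1.1 does not. Its worsening clause concerns preexisting events, and the same section ties that word to onset before consent. An AE that began in screening is outside it.
- Sections 6.4.10.3 and 6.4.10.10 are broader and point toward recording the worsening. For an event that is already an AE, neither says that a second record is needed or which onset date it carries.
- Section 7.3 lists the items recorded for an AE, including onset and resolution dates and severity. It gives no rule for a severity change within an open AE.
- Section 7.5 follows an AE until it resolves or stabilises, which is compatible with one continuing record.

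Case 4 is therefore permitted, and nothing later in SAP 9.1 recovers it. The maximum-severity table works only on events already classed as TEAEs. The serious, related and discontinuation tables carry the same restriction.

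**The case against.** The strongest reply is that the protocol already requires worsening to be recorded as an AE. If sites read 6.4.10.3 as calling for a separate entry, the existing definition counts it. This has real force. A reader might infer that any screening AE that worsens on drug is lost from the tables, and the documents do not support that: the loss arises only where the worsening stays on the original record. CRF completion guidelines are not among the documents and may settle the matter. What survives is that no visible text does.

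Second, much would still be seen elsewhere. Supine and seated blood pressure with outlier counts (SAP 9.5), supine ambulatory pressure by treatment and visit (9.5.1) and ECG outliers (9.6) are all summarised. SAEs are listed (protocol 8.6.2), as are AEs leading to discontinuation (SAP 9.1). Protocol 8.6.2 also plans to list and summarise events of special interest without restricting them to TEAEs. This reduces the harm, but listings and vital-sign tables do not replace AE incidence by arm.

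Third, SAP 9.1.1 (events of special interest) and SAP Appendices 1 and 2 are redacted, and a rule could sit there. The main TEAE definition is nevertheless visible in full.

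Fourth, the ECG comparison is imperfect. ECG findings are visit measurements judged against baseline, whereas AEs carry onset dates. It shows that the protocol has suitable wording, not that the AE rule contradicts it.

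**Conclusion.** The point stands in conditional form. The definition is onset-only in both documents, and the SAP keeps pre-dose AEs out of the summaries. Unless the site opens a new record, on-drug worsening of a screening-period AE is left out of the TEAE tables. This rests on the visible text only, with the redactions noted above. It does not touch the efficacy analyses.

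Three stronger readings are tempting and not supported:

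- **A percentage of subjects affected, set against the SAP's 3% cut-off for frequent TEAEs.** The documents give no rate of screening AEs, of worsening, or of single-record practice. A subject who loses one TEAE may also still be counted through another. The size cannot be estimated.
- **That the loss falls mainly on the active arm.** Worsening caused by the drug can occur only there, but worsening from disease or from withdrawal of earlier treatment can occur in both arms. Withdrawing pressor drugs would also be expected to produce low-pressure symptoms rather than supine hypertension. No passage establishes a difference between arms.
- **That protocol 7.3 fixes one severity per AE record.** It only lists items to be recorded. If it did fix one severity, a change would more naturally call for a second record.

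**What to change.** In SAP 9.1, define a TEAE as any AE that starts, worsens in severity or frequency, or becomes serious on or after first dose and up to 14 days after the last dose. Keep the existing Study 0170 exception. Restrict listing-only treatment to pre-dose AEs that do not worsen after dosing starts. State in the CRF completion guidelines that when an AE with pre-dose onset worsens after first dose, the worsening is entered as a new AE record dated from the day of worsening. If such a rule already exists, cite it in SAP 9.1.

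The cost is a short change to SAP 9.1 and a line of CRF guidance before database lock. TEAE counts may rise slightly, and sites must date the worsening.

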9.2. Extent of Exposure and Treatment Compliance

Duration of study drug exposure (days) will be summarized. Duration of exposure to study drug is calculated as (date of last dose – date of first dose + 1).

Subjects will receive their assigned dose (10-mg dose of amprelosetine (TD-9855) or matching placebo) once daily. Treatment compliance as a percentage of the expected total dose will be calculated as follows, using the information captured on the CRF page for “Study Drug Dispensing / Return”:

- $100 \times (\text{number of tablets dispensed} - \text{number of tablets returned}) / (\text{date of last dose} - \text{date of first dose} + 1)$

Treatment compliance as a percentage of expected total dose will be summarized by treatment group for the safety analysis set as a continuous variable and using the following categories, after rounding to the nearest 0.1%:

- $\geq 120\%$
- $\geq 80\% - < 120\%$
- $< 80\%$

Study drug administration (date/time and study day) and drug accountability data will be listed.

9.3. Concomitant and Other Medications

Medications will be coded using the World Health Organization Drug Dictionary (WHODD, 3Q 2020 C3). Medications entered on the case report form will be mapped to Anatomic Therapeutic Chemical (ATC) drug class and generic drug name. Each verbatim name will be classified by anatomical main group (ATC level 1), therapeutic subgroup (ATC level 2), pharmacological subgroup (ATC level 3), chemical subgroup (ATC level 4), and preferred name (ATC level 5, chemical substance).

Prior medications are medications used before initiation of study drug. Concomitant medications are medications used after initiation of study drug, including ongoing prior medications and medications beginning up to 14 days after the last dose of study drug.

The number and percentage of subjects receiving prior and concomitant medications will be summarized by treatment group, medication class and standardized medication name (preferred name) for the safety analysis set. ATC level 4 is generally used to determine the medication class for a medication. If ATC level 4 is not available, the next available level of ATC code (i.e., level 3, level 2, or level 1) will be used. Subjects reporting use of more than one medication at each level of summarization (any medication received, ATC class, and preferred name) will be counted only once.

Summaries of prohibited prior medications will be provided.

On-treatment midodrine usage will be summarized for days of midodrine usage and daily dosage (mg) of midodrine. For days of midodrine usage, counts and percentages will be provided for the following categories:

- 0
- 1
- 2
- 3
- 4
- ≥ 5

Numbers and percentages of subjects who took midodrine on assessment days will be provided.

Listings of prior medications, concomitant medications, and midodrine usage will be provided.

9.4. Laboratory Data

Quantitative hematology, serum chemistry and urinalysis test results will be summarized in terms of observed values and changes from baseline for each visit. In addition, changes from baseline for each visit relative to normal ranges (e.g., shifts from normal to abnormal high/low) will be summarized in shift tables for hematology and serum chemistry.

Listings will flag laboratory values that are outside the normal range, and listings of all abnormal laboratory values will be provided.

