14. Subject has known congestive heart failure (New York Heart Association [NYHA] Class 3 or 4).

15. Subject has any malignant disease other than carcinoma in situ of the cervix or basal cell carcinoma within the past 2 years prior to screening.
16. Subject has a known gastrointestinal (GI) condition, which in the Investigator's judgment, may affect the absorption of study medication (e.g., ulcerative colitis, gastric bypass).
17. Subject has psychiatric, neurological, or behavioral disorders that may interfere with the ability of the subject to give informed consent or interfere with the conduct of the study.
18. Subject is currently receiving any investigational drug or has received an investigational drug within 30 days of dosing. An investigational drug is defined as nonregulatory agency approved drug (e.g., Food and Drug Administration).
19. Subject has a clinically significant abnormal laboratory finding(s) (e.g., alanine aminotransferase [ALT] or aspartate aminotransferase [AST] >3.0 x upper limit of normal [ULN]; blood bilirubin [total] >1.5 x ULN; estimated glomerular filtration rate (eGFR) <30 mL/min/1.73m^2, or any abnormal laboratory value that could interfere with safety of the subject).
20. Subject has demonstrated a history of lifetime suicidal ideation and/or suicidal behavior, as outlined by the C-SSRS (Baseline/Screening Version) subject should be assessed by the rater for risk of suicide and the subject's appropriateness for inclusion in the study.
21. Subject has a concurrent disease or condition that, in the opinion of the Investigator, would confound or interfere with study participation or evaluation of safety, tolerability, or pharmacokinetics of the study drug.
22. Subject has known hypersensitivity to TD-9855 (amprelosetine hydrochloride), or any excipients in the formulation.
23. Subject has (i) confirmed severe acute respiratory syndrome coronavirus 2 (SARS-CoV-2) documented with coronavirus disease 2019 [COVID-19] positive test result, OR (ii) is suspected of SARS-CoV-2 infection (clinical features without documented test results two weeks after resolution of symptoms and remains asymptomatic until Day 1), OR (iii) has been in close contact with a person with known (or suspected) SARS-CoV-2 infection and remains asymptomatic until Day 1.

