##### **6.4.10.9.2. Chemistry**

Chemistry samples will be analyzed for the following: sodium, potassium, calcium, chloride, bicarbonate, glucose, blood urea nitrogen, creatinine, eGFR, total protein, albumin, alkaline phosphatase, ALT, AST, bilirubin, lactate dehydrogenase, and creatine phosphokinase.

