#### 8.6.4. Laboratory Data

Laboratory values, changes from baseline, values relative to normal ranges, and values and changes meeting specified criteria, will be summarized.

Reference ranges provided by the laboratory for each test will be used to evaluate the clinical significance of laboratory test results. Values falling outside the relevant reference range will be flagged, as appropriate, in the data listings. Abnormalities in clinical laboratory test results will be listed in a separate listing.

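### SAP 9.4 has no counterpart to the criteria-based laboratory summary promised in protocol 8.6.4, so no planned table gives an objective count by arm of marked laboratory abnormalities

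*SAP*

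**What the plan says.** Protocol 8.6.4 commits to four things: "Laboratory values, changes from baseline, values relative to normal ranges, and values and changes meeting specified criteria, will be summarized". It attaches no cut-offs to the fourth.

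SAP 9.4 shows no redaction. It opens with "Quantitative hematology, serum chemistry and urinalysis test results will be summarized in terms of observed values and changes from baseline for each visit". It adds shift tables for hematology and serum chemistry, in which "changes from baseline for each visit relative to normal ranges (e.g., shifts from normal to abnormal high/low) will be summarized in shift tables". It ends with "Listings will flag laboratory values that are outside the normal range, and listings of all abnormal laboratory values will be provided".

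Four other places bear on this:

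- SAP Section 2 makes the SAP the final authority on analyses. Protocol 8.1 requires changes to the planned summaries to be described in the SAP.
- SAP 9.5 (Table 8) and SAP 9.6 (Table 9) plan outlier counts for vital signs and ECG.
- Protocol 8.6 lists unscheduled quantitative safety data but leaves them out of summaries. Unscheduled categorical data do enter summaries that cover the whole treatment period.
- SAP 6.3.4 and 6.3.5 assign laboratory results to a Week 2 window (study days 2 to 21) and a Week 4 window (study days 22 to 42), and in general keep the record closest to the nominal day.

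**The concern.** The fourth commitment is the one that would separate a trivial excursion from a marked one. Protocol 6.4.10.9.2 collects "alkaline phosphatase, ALT, AST, bilirubin, lactate dehydrogenase, and creatine phosphokinase", along with creatinine and eGFR, so the data for such a summary exist. As SAP 9.4 is written, a reader comparing the arms would see central tendency and movement across the edge of the normal range. The reader would not see how many subjects in each arm went far beyond it. At stake is whether a small cluster of marked liver or renal abnormalities in one arm shows up in a planned table or has to be found by reading individual records.

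**Working it through.** No figure in the plan underlies this point, so the check is a comparison of text plus a short classification exercise.

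**Step 1. Protocol 8.6.4 against SAP 9.4.**

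| Protocol 8.6.4 item | Visible SAP 9.4 |
|---|---|
| Values | Yes, by visit |
| Changes from baseline | Yes, by visit |
| Values relative to normal ranges | Yes, shift tables (hematology, chemistry) |
| Values and changes meeting specified criteria | No counterpart |

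The listings flag values outside the normal range. They are not counts.

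**Step 2. Parallel safety domains.** Protocol Tables 2 and 3 give thresholds for vital signs and ECG, and the SAP carries both over. SAP Table 8 also has a heart-rate row (>120) that protocol Table 2 lacks. Laboratory data are the domain left without a threshold count.

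**Step 3. What a low/normal/high shift table separates.** ALT values below are assumed, in multiples of ULN.

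| Baseline | Post-baseline | Shift cell | Above 3 x ULN? |
|---|---|---|---|
| 0.8 | 1.05 | normal to high | no |
| 0.8 | 4.0 | normal to high | yes |
| 0.8 | 10.0 | normal to high | yes |
| 1.2 | 1.3 | high to high | no |
| 2.9 | 9.0 | high to high | yes |

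Within each cell, small and large rises look the same.

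**Step 4. Whether the means help.** SAP 4.4 says at least 40% of subjects, at least 76, will have MSA, with 1:1 allocation. That implies 76 / 0.40 = 190 subjects, or 190 / 2 = 95 per arm (inferred, since the sample size is redacted). One subject rising from 0.8 to 4.0 x ULN moves the arm mean change by (4.0 - 0.8) / 95 = 0.034 x ULN. The mean would not reveal it.

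**Step 5. Which draws reach the by-visit summaries.** Protocol Table 1 schedules on-treatment safety laboratory tests at Day 15 and Day 29/ET. Dosing starts on Day 2, so these are study days 14 and 28 in SAP terms. Protocol 6.4.10.9 allows repeat and additional tests. Suppose a Day 15 draw on study day 14 is followed by an extra draw on study day 18 that shows the peak.

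- Under protocol 8.6, the extra draw is listed and not summarized.
- Under SAP 6.3.4 and 6.3.5, which ignore visit labels, both draws fall in the study day 2 to 21 window. The distances from day 14 are 0 and 4, so the study day 14 record is kept.

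Either way the peak is absent from that visit's mean, maximum and shift table. Under the SAP rule, an early-termination draw on study day 18 would be displaced in the same way.

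**Step 6. Other routes to the information.**

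- Adverse events: protocol 7.2 requires abnormalities that are symptomatic or that the investigator judges clinically significant to be recorded as adverse events if they meet the definition. SAP 9.1 counts treatment-emergent events by arm. This depends on judgement, not on a fixed limit.
- By-visit maximum: it is part of the 8-point summary in protocol 8.1. It shows one extreme value per arm and visit, not a number of subjects, and only if the record was selected.
- Listings: complete, but uncounted.

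**The case against.** The strongest case on the other side has four parts.

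**Marked abnormalities are not hidden.** A reader might infer that they would appear only in listings. The documents do not support that: clinically significant findings reach the adverse event tables by arm, and a 10 x ULN value would show as a by-visit maximum if its record is selected. This part stands. It limits the point to the lack of an objective, fixed-threshold count.

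**Sampling is not capped at two draws.** Two draws are scheduled, but protocol 6.4.10.9 and 6.4.10.12 allow more. This stands as a correction to any claim that subjects have at most two. It does not rescue the by-visit tables, which can omit those extra draws.

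**No defined threshold set has been lost.** Protocol 8.6.4 gives no laboratory cut-offs and does not mention ALT. Its only stated yardstick is the laboratory reference range, which SAP 9.4 uses. Exclusion criterion 19, with "aspartate aminotransferase [AST] >3.0 x upper limit of normal [ULN]; blood bilirubin [total] >1.5 x ULN", gives eligibility examples and contains no change criterion. A reader might take those limits for the protocol's analysis criteria, but nothing in the documents makes them so. This stands: what is missing is a commitment to a type of summary, and the criteria remain the sponsor's to set.

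**Redaction leaves room for doubt.** SAP Appendix 1, which records changes to protocol-planned analyses, is redacted, as are SAP 9.1.1 and most of Appendix 2. The SAP abbreviation list defines ALT, ULN and LLN, which the visible text does not otherwise use. A reader might infer that the removal is undocumented, but that cannot be said. However, a note in Appendix 1 recording a removal would disclose the departure without restoring the summary to SAP 9.4.

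**Conclusion.** The point holds as a gap between protocol 8.6.4 and visible SAP 9.4. Three of four promised laboratory summaries are planned, and the fourth is not. Followed as written, the plan yields no objective count by arm of subjects with marked laboratory abnormalities, and the partial routes do not replace one.

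The size is small. The missing output is descriptive, needs no new data and does not touch the primary analysis or the error rate. No number of affected subjects can be given, because the documents contain no laboratory event rates. The ALT values and the study day 18 draw are illustrations, and the arm size of 95 is inferred from the MSA quota.

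The conclusion assumes that no redacted section or unseen table shell supplies the count.

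**What to change.** Add to SAP 9.4 a table giving, by arm, the number and percentage of subjects in the safety analysis set whose worst on-treatment value or change from baseline meets laboratory criteria that the sponsor prespecifies.

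- State that unscheduled values are included. This is needed because protocol 8.6 otherwise only lists unscheduled quantitative data. Its treatment of unscheduled categorical data over the whole treatment period is a ready precedent.
- The limits in exclusion criterion 19 (ALT or AST >3 x ULN, total bilirubin >1.5 x ULN, eGFR <30 mL/min/1.73m²) can serve as a default set, for reporting only. They carry no implication for managing subjects.
- Add criteria for change, since the protocol commitment covers changes as well as values.
- A row for concurrent ALT/AST and bilirubin elevation is optional.

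If the summary was left out on purpose, state and justify that as a change from the protocol, as protocol 8.1 requires.

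The cost is a few sentences of SAP wording and one descriptive table on data already collected.
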